## **B. METHODS**

The specific goal of this study is to assess the frequency of AF in patients with OSA using a cardiac event monitor ([www.lifewatch.com](http://www.lifewatch.com)). We will specifically target OSA patients with a CHADS score of  $\ge 2$ .

Patients who are newly diagnosed with OSA (within the last 12 months) based on a PSG at one of our participating hospitals will be eligible. Patients with a CHADS score of  $\ge 2$  will be approached for evaluation with a two week cardiac event monitor. The target sample size is 200 patients. The rationale for this sample size is provided below.

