#### **Outcome Measures**

After completion of the four week cardiac event monitor, we will record the frequency of abnormalities such as:

1. Frequent premature atrial contractions
2. Frequent ventricular premature contractions
3. Definite AF (defined as an irregularly irregular rhythm with absence of p waves)
4. Longest duration of AF
5. AF episodes lasting more than six minutes

Initial interpretation of the cardiac monitor is provided by Lifewatch technicians and the reports will be confirmed by the study assigned cardiologist. The Lifewatch technicians receive ECG information only and no identifiable information. We will follow patients for six months after the placement of the cardiac event monitor. We will document selection of antithrombotic therapy including the following:

1. Novel oral anticoagulant (NOAC)
2. Warfarin
3. Antiplatelet therapy
4. No antithrombotic therapy

After all patients have completed the six month follow-up period, we will record the following:

1. Frequency of undetected AF
2. AF frequency according to baseline CHADS score
3. Rate of utilization of anticoagulants in patients with AF
4. Rate of utilization of antiplatelet therapy in patients with AF
5. Predictors of AF based on baseline variables (age, sex, history of CHF, BMI, etc.)

If we find that >5% of patients with OSA and CHADS score of  $\geq 2$  have undetected AF, then this would support a larger multi-center study of screening OSA patients for AF and identifying predictors of AF in this population.

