### **C. SAMPLE SIZE CONSIDERATIONS**

The frequency of AF in the general population is likely to be <1%. Our hypothesis is that 5% of OSA patients screened with a four week monitor will have AF.

If  $p$  = the percent of patients with sleep apnea who have afib, then the z-test will assess the following hypotheses:

$H_0: p \leq 1\%$

$H_1: p > 1\%$

If the true value of  $p$  is 5%, then a study with 200 patients has power = 97%. That is, the probability is 0.97 that the null hypothesis ( $H_0$ ) will be rejected at a significance level of 5% in favor of the alternate hypothesis ( $H_1$ ).

The sample size needed for 80% power is 59 patients. The higher sample size is justified since the point estimate of AF frequency will be more precise with the larger sample size. Further, analysis of the predictors of AF according to baseline variables will be more fruitful with a larger sample size.

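### Is the 200-patient target wrongly justified by a predictor analysis when only about 10 AF cases are expected?

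*Combined protocol and SAP*

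**What the plan says.** "The target sample size is 200 patients" (section B, Methods). Section C states the working assumption, "Our hypothesis is that 5% of OSA patients screened with a four week monitor will have AF", and tests it one-sided against 1%: "then a study with 200 patients has power = 97" per cent, with 59 patients enough for 80% power. It then gives two reasons for going beyond 59. The first is a more precise estimate of AF frequency. The second is that "analysis of the predictors of AF according to baseline variables will be more fruitful with a larger sample size".

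The predictor analysis itself appears under Outcome Measures as the last of five items to be recorded after follow-up: "Predictors of AF based on baseline variables (age, sex, history of CHF, BMI, etc", with the list left open. A separate item is "AF frequency according to baseline CHADS" score. The plan names no regression model, selection procedure, detectable effect, expected number of cases or exploratory label for either item. Outcome Measures and section J (Future Directions) say what would support a larger study. Both use the AF frequency, set at 5%, and neither uses a predictor result. Outcome Measures lists finding predictors among the purposes of that later study.

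**The concern.** A sample size argument normally rests on something the sample can deliver. Here one of the two reasons for enrolling 141 patients beyond 59 (200 − 59) is an analysis with about 10 events and at least four candidate variables. A conventional four-variable logistic model on such data can separate or give wildly varying estimates. Searching an open list after seeing the data could also turn up chance predictors. OSA severity, which the qualifying sleep study would provide, is not among the named variables. If these results were presented as firm, they could misdirect the choice of candidates for the follow-on study or for the prediction score mentioned in section J.

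**Working it through.** **Inputs from the plan.** N = 200; AF frequency 5% under the alternative and 1% under the null; one-sided 5% test; 59 patients for 80% power (section C). Four named predictors (Outcome Measures). Dropout below 2% (section F).

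**The plan's own figures.**
- Null standard error at N = 200: √(0.01 × 0.99 / 200) = 0.00704. Rejection limit: 0.01 + 1.645 × 0.00704 = 0.0216, a count of 4.31, so the test rejects at 5 or more cases.
- Normal-approximation power: Φ[(0.05 − 0.0216) / √(0.05 × 0.95 / 200)] = Φ(0.0284 / 0.0154) = 0.967. Exact binomial power for 5 or more cases is 0.974. Both agree with 97%.
- At N = 59 the limit is a count of 1.85, so the test rejects at 2 or more cases. Exact power is 0.801, which agrees with the stated 80%.

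**Expected cases.**
- 200 × 0.05 = 10 (95% binomial range 4 to 16); with 2% dropout, 196 × 0.05 = 9.8.
- 59 × 0.05 = 2.95 (range 0 to 7).
- Cases per predictor with four predictors: 10 / 4 = 2.5 (1.0 to 4.0 over the range 4 to 16). For scale, ten cases per predictor would need 40 / 0.05 = 800 patients.

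**Detectable effects at N = 200** (one predictor, two-sided 5%, 80% power, overall AF frequency held at 5%; predictor prevalences are assumptions).
- Continuous: exp[(1.96 + 0.84) / √(200 × 0.05 × 0.95)] = exp(2.80 / 3.08) = 2.48 per standard deviation. At N = 59 the same formula gives 5.33.
- Binary, 50% prevalence, normal approximation: group risks of 0.7% and 9.3% (odds ratio 14.4) give Φ[(0.0858 − 1.96 × 0.0308) / 0.0302] = Φ(0.84) = 0.80. The more conservative Fisher test has 73% power at odds ratio 12 and 82% at 20.
- Binary, 20% prevalence: odds ratio 6.8 by normal approximation; Fisher power is 83% at 8.
- Fisher p-values for 10 cases in two groups of 100: a 9-to-1 split gives 0.018, an 8-to-2 split 0.10.
- At N = 59, normal approximation, a predictor present in half the patients does not reach 80% power at any odds ratio up to 5,000 (42% there).

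**Stability, if a four-variable maximum-likelihood logistic model were fitted.** All effect sizes and prevalences here are assumptions.
- Odds ratios 1.8 (age), 2 (sex), 2.5 (CHF) and 1.5 (BMI), 60% male, 15% with CHF: about 12% of simulated trials failed or separated. With 30% CHF the figure is about 8%.
- Weaker effects and 10% CHF: about 19% to 21%.
- In the weaker-effect runs that could be fitted, power was 6% to 23% per predictor. The estimated sex odds ratio ranged from 0.36 to 8.3 (middle 95%) around a true 1.5.

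**The first reason for 200, taken alone.** The 95% half-width at 5% is 1.96 × √(0.05 × 0.95 / 200) = 3.0 percentage points, against 1.96 × √(0.05 × 0.95 / 59) = 5.6 points with 59 patients.

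**The case for a change.** The strongest case for a change is that the plan cites this analysis as a reason to enrol more patients without stating that about 10 cases are expected. Ten cases cannot detect moderate effects even one variable at a time: Fisher power for a predictor present in half the patients is 23% at odds ratio 3. An open list with no stated method leaves room for selection after the data are seen. A few words of analysis text (an exploratory label, a short named list, penalised estimation) would cost almost nothing.

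The arithmetic stands, and so does the observation that event count, method and label are missing. The rest is weaker:

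- The unstable four-variable model and the data-driven search are not in the plan. The CHADS2 item is a descriptive breakdown, not another model term.
- The claim that such a model often fails rests on about 12% of runs under one set of assumptions, and roughly 8% to 21% across those tried.
- The claim that only very large effects are detectable fits binary predictors. Age and BMI, if analysed as continuous, have a detectable effect of about 2.5 per standard deviation.
- OSA severity may fall under the open list, and the content of the baseline form is not shown, so its omission cannot be inferred.
- One-at-a-time penalised models with a linear CHADS2 score are one defensible choice among several. They would replace no stated method.

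**Conclusion.** The event count is as low as feared, but no change to the plan follows. The quoted sentence compares 200 with 59 patients, and that comparison is correct: about 10 cases against 3, and a detectable odds ratio per standard deviation of 2.5 against 5.3. It commits the study to nothing that the design fails to deliver. Precision supports 200 without it (half-width 3.0 against 5.6 percentage points). The AF estimate, the z-test, its 97% power and the 5% criterion for a larger study do not depend on predictors. What is missing is detail that an analyst with about 10 cases would fill in sensibly, by reporting simple estimates with wide intervals as exploratory.

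This rests on the plan's 5%. Section C and Outcome Measures refer to four weeks of monitoring, while Methods and the device description give two; those passages must be reconciled, and a shorter recording could only lower the yield. If the frequency were 10% instead (an assumption), 20 cases would give 5 per predictor, still few enough for the analysis to be exploratory.

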#### **D. Performance sites**

Patients with OSA will be identified and recruited for the study at The University of Miami Sleep Center, which is accredited by the American Academy of Sleep Medicine. (<http://uhealthsystem.com/sleep-center>). The UM Sleep Center has an eight bed sleep lab and performs over 1000 sleep studies per year and diagnoses over 500 patients per year with OSA. There is ample volume of clinical patients for study recruitment.

#### **E. Study Procedures and Timeline**

See Table 1

#### **F. Data Management Plan**

The Department of Neurology at the University of Miami Miller School of Medicine has a full time statistician and has served as the clinical coordinating center for previous multi-center trials. The research infrastructure is excellent. The Neurology Department participates in two major NIH-sponsored clinical trial consortia, the NeuroNext Initiative and the Stroke Trials Network (StrokeNet).

With regard to data collection and adequacy, data will be obtained directly from the study participants via office visits or through phone follow-up, and thus we feel that the data source for those elements will be quite accurate. The electronic medical record (EMR) at the two facilities will be another source for obtaining information on any medical encounters for cardiac issues such as atrial fibrillation. Electronic case report forms will be created for data collection in the study.

Although all measures will be undertaken to prevent missing data, it is likely that there will be some missing data elements due to patients who drop out of the study. Due to the relatively short duration of study participation and the patient stipend being offered, we expect a dropout rate of <2%. To handle missing data, we will first examine the characteristics of those who are missing outcome data compared to those who are not, as well as those who were lost-to-follow-up and those who were not, to determine whether there are differences in important characteristics between the groups (e.g. age, race). To deal with missing data in the outcome, we will employ methodology such as the use of multiple imputation.

#### **G. Drug Supply Request**

None

#### **H. Adverse Events**

### **MANAGEMENT AND REPORTING OF ADVERSE EVENTS/ADVERSE REACTIONS**

#### **1.1 DEFINITIONS OF ADVERSE EVENTS**

Adverse event

An adverse event (AE) is defined as any untoward medical occurrence in a patient or clinical investigation subject administered a medicinal product and which does not necessarily have a causal relationship with this treatment. An adverse event can therefore be any unfavorable and unintended sign (e.g. an abnormal laboratory finding), symptom, or disease temporally associated with the use of a medicinal product, whether or not considered related to the medicinal product.

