#### *Risk/benefit considerations*

No benefit can be guaranteed to study participants. However, if they do have early detection of AF, they can be placed on appropriate antithrombotic treatment to prevent stroke, which is a potential benefit.

There are no major risks with the device. Some patients may have skin irritation and special "sensitive skin" leads are available for these patients. There is no restriction with the use of the device with pacemakers or other implanted devices since only surface recordings are made.

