### **Adverse reaction (ADR)**

An adverse reaction is defined as a response to a medicinal product which is noxious and unintended. Response in this context means that a causal relationship between a medical product and an adverse event is at least a reasonable possibility. Adverse reactions may arise from use of the product within or outside the terms of the marketing authorization or from occupational exposure. Conditions of use outside the marketing authorization include off-label use, overdose, misuse, abuse and medication errors.

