### **Serious adverse event**

A serious adverse event is defined as any AE which

- results in death,
- is life-threatening,
- requires in-patient hospitalization, or
- prolongation of existing hospitalization,
- results in persistent or significant disability or incapacity, or
- is a congenital anomaly/birth defect

Life-threatening in this context refers to a reaction in which the patient was at risk of death at the time of the reaction; it does not refer to a reaction that hypothetically might have caused death if more severe.

Medical and scientific judgement should be exercised in deciding whether other situations should be considered serious reactions, such as important medical events that might not be immediately life threatening or result in death or hospitalization, but might jeopardize the patient or might require intervention to prevent one of the other outcomes listed above. Examples of such events are intensive treatment in an emergency room or at home for allergic bronchospasm, blood dyscrasias or convulsions that do not result in hospitalization or development of dependency or abuse. Any suspected transmission via a medicinal product of an infectious agent is also considered a serious adverse reaction.

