### **1.3 ADVERSE EVENT REPORTING TO BOEHRINGER-INGELHEIM (BI)**

**Dabigatran is not part of the protocol but the following section is added at the request of the sponsor in case patients receive dabigatran.**

INSTITUTION shall report

- (i) all ADRs, serious and non-serious
- (ii) all fatal AEs
- (iii) pregnancies in female subjects and partners of male subjects

which are associated with dabigatran by fax the BI Unique Entry Point ([contact]) using BI NIS SAE report form in following timelines.

All Serious ADRs and AEs with fatal outcome shall be forwarded immediately (within twenty four (24) hours or next business day whichever is shorter).

All non-serious ADRs shall be forwarded within seven (7) days

The investigator carefully assesses whether an AE constitutes an ADR using the information below.

Causal relationship of adverse event

The definition of an adverse reaction implies at least a reasonable possibility of a causal relationship between a suspected medicinal product and an adverse event. An adverse reaction, in contrast to an adverse event, is characterized by the fact that a causal relationship between a medicinal product and an occurrence is suspected.

Medical judgment should be used to determine the relationship, considering all relevant factors, including pattern of reaction, temporal relationship, de-challenge or re-challenge, confounding factors such as concomitant medication, concomitant diseases and relevant history.

Reporting of related Adverse Events associated with any other BI drug

The investigator is encouraged to report all adverse events related to any BI drug other than dabigatran according to the local regulatory requirements for spontaneous AE reporting at the investigator's discretion by using the locally established routes and AE report forms.

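### Section H defines adverse events by use of a medicinal product in a study that gives no drug, so monitor-related events cannot be classified or counted consistently

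*Combined protocol and SAP*

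**What the plan says.** **Definitions (Section H, 1.1 and the two definitions after it).** An AE is "any untoward medical occurrence in a patient or clinical investigation subject administered a medicinal product". Its timing is tied in the same way: the sign, symptom or disease must be "temporally associated with the use of a medicinal product, whether or not considered related to the medicinal product". For reactions, "An adverse reaction is defined as a response to a medicinal product which is noxious and unintended". The serious category is built on the first definition: "A serious adverse event is defined as any AE which" meets one of the listed criteria.

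**What the study gives.** Under "Drug Supply Request" (Section G) the entry is none. Section H, 1.3 says "Dabigatran is not part of the protocol" and explains that its reporting rules were added at the sponsor's request in case a patient receives the drug. Section B (Treatment Plan and Dosing Regimen) has the study screen with the monitor and record antithrombotic drugs used in outpatient care.

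**The device.** Section B describes a chest-worn sensor with four electrodes on a harness. Under Risk/benefit considerations it sees no major risks, but says "Some patients may have skin irritation" and offers leads for sensitive skin.

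**Collection.** Appendix One has staff ask about adverse events at the 1-week contact. Section H, 1.2 places a duty on the institution and investigator to report AEs arising while the study runs.

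**The concern.** The safety definitions come from a drug trial and do not fit a device-screening study. Section H never mentions the monitor. The one thing the protocol does to every subject therefore has no place in the rules that say what counts as an adverse event and what it may be related to.

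The consequence is inconsistent classification. Staff will ask about adverse events while the monitor is on, hear about skin reactions, and find that the protocol does not tell them how to class those reactions. Section B (Outcome Measures) says the result may support a larger multi-center screening study. How well the monitor is tolerated would be useful to that study, and the present definitions cannot give a dependable count of device-related events.

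**Working it through.** The plan states no figure on this point, so the check is to apply each definition to the same event.

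**Inputs**
- AE: needs a subject given a medicinal product, with timing linked to its use; cause is irrelevant (Section H, 1.1).
- ADR: needs a response to a medicinal product (Section H, Adverse reaction).
- SAE: an AE that also meets a seriousness criterion (Section H, Serious adverse event).
- Study drug: none (Sections G and H, 1.3).
- Intervention: the monitor, worn by all 200 planned subjects (Section B).

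**Applying the definitions to an electrode skin reaction**

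| Subject at the time | AE? | SAE, if serious? | Category for relatedness to the monitor? |
|---|---|---|---|
| Taking some medicine, for any reason | Yes, read literally | Yes | None |
| Taking no medicine | No | No | None |

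1. The AE column changes between the rows although the event and its cause are the same. What changes it is medication unconnected with the study.
2. The SAE column follows the AE column, because an SAE is a subset of AEs.
3. The last column is empty in both rows. The reaction definition refers only to medicinal products, and the causality guidance in 1.3 also speaks only of a suspected medicinal product. The reaction text once uses the looser term medical product, but its defining sentence says medicinal product and it goes on to overdose and medication errors. That one variant does not bring in a monitor.

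**Can the gap be counted?** Let r be the proportion of subjects with skin irritation, and m the proportion of those subjects who are taking any medicine at the time.
- Subjects whose irritation falls outside the AE definition: 200 × r × (1 − m).
- Subjects whose irritation has no category for relatedness to the monitor: 200 × r.

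The documents give neither r nor m. The first quantity runs from 0 (m = 1) to 200 × r (m = 0), so no number can be stated. The second does not depend on m.

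**The case against.** **The stronger reading.** A reader might infer that every device event lies outside the AE and SAE rules because no subject receives a study drug. The documents do not support that. The definition says a medicinal product, not a study product, and covers events whether or not related to it. A rash in a subject taking any medicine is therefore literally an AE. Enrolment requires a CHADS score of at least 2, and Section J describes hypertension and diabetes as frequent in this population. Background medication is not reported but is plausibly common. This objection stands, and it limits the AE and SAE gap to subjects on no medicine. It does not touch the missing relatedness category, and it confirms that AE status turns on an irrelevant fact.

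**Capture in practice.** A reader might also infer that the study would report few or no AEs. That does not follow either. The week-1 contact asks about adverse events, 1.2 requires reporting, and nothing tells staff to discard device complaints. This stands as to enquiry. But both places use the term AE without widening it, so how a complaint is classed is left to individual judgement.

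**Low stakes.** Section B says the device is already in routine use at both hospitals. Tolerability is not a listed outcome, and the stated trigger for a larger study is AF frequency above 5%. All of this is correct. Skin irritation will also seldom be serious.

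**Conclusion.** The point holds as a mismatch between the stated definitions and the intervention. It has two parts:

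- AE status of a monitor-related event, and SAE status if it is serious, depends on whether the subject happens to take some medicine.
- No subject's event can be assigned relatedness to the monitor under Section H.

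The second part applies to all 200 planned subjects. The first applies to those on no medicine, whose number the documents do not give. The conclusion rests on the literal text and needs no assumed irritation rate.

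The AF frequency estimate, the hypothesis test and the sample size are unaffected, and the point is not evidence of an urgent hazard. It deserves correction because a rule is written down, does not fit the study, and can be repaired cheaply.

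**What to change.** 1. In Section H, 1.1, define an AE as any unfavorable medical event in an enrolled subject that arises in association with wearing the study monitor, from placement to removal, or with use of a medicinal product, regardless of suspected cause.
2. Leave the SAE criteria as they are; they will follow from the new AE definition.
3. Add to 1.1 an assessment of relatedness to the monitor, separate from the medicinal-product reaction definition.
4. At the existing week-1 contact, record skin irritation, and any early removal it causes, as device-related AEs.
5. Leave 1.3 unchanged. It governs dabigatran reports, and relatedness to the device does not belong there.

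The window is tied to wear and not to the six-month close-out because Appendix One lists an AE question only at week 1. A longer window would bring in intercurrent hospitalizations with no step to collect them. One limit remains: the week-1 contact falls before monitoring ends, so later skin reactions would be recorded only if the subject volunteers them.

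The cost is a change of protocol wording, an eCRF field and a few more minor AEs on record. No treatment, endpoint or sample size changes.
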